# STUDY PROTOCOL

## Background

Fulminant hepatic failure (FHF) (alternatively, acute liver failure [ALF]) is a rare but life-threatening critical illness that occurs most often in patients who do not have a preexisting liver disease. It is the clinical manifestation of liver cell death of a critical degree with insufficient hepatocellular regeneration and is characterized by hepatic encephalopathy and/or coagulopathy. The mortality rate without liver transplantation (LT) is over 40% in patients with acetaminophen-induced FHF and 80% in those with nonacetaminophen-related FHF. This 80% decreases to 30% when LT and artificial liver support system are available. Hepatitis A virus (HAV) is considered to be the commonest cause of acute viral hepatitis worldwide. In acute infection with HAV, a cellular immune response attacking virus-infected cells is responsible for the clinical manifestations and the recovery mediated by CD8+ T cells and CD4+ T cells, in addition to B cell response producing immunoglobulin [Ig]M and IgG according to the time-course of the disease. HAV infection can cause FHF and death in about 0.2% of clinical cases. Extensive destruction of infected hepatocytes by T cell-mediated lysis was supposed to be the cause of FHF. Hepatitis A virus (HAV) is the most common cause of acute viral hepatitis worldwide. In acute HAV infection, a cellular immune response attacking virus-infected cells is responsible for the clinical manifestations and the recovery mediated by CD8+ T cells and CD4+ T cells, in addition to B cell response producing immunoglobulin [Ig]M and IgG according to the time-course of the disease. Although rare, HAV infection can cause FHF and death in approximately 0.2% of clinical cases. Overwhelming elimination of infected hepatocytes by T cell-mediated lysis was supposed to be the cause of FHF.

## **Material and methods**

### ***Study population:***

This study included 26 children with fulminant hepatitis A. They were recruited over a period of 4 years duration and divided into two groups. Group one is comprised of 18 children with fulminant HAV infection who received steroid therapy beside standard supportive measures (steroid group). The second group is comprised of 15 children with fulminant HAV infection who did not receive steroid therapy, but only standard supportive measures (non steroid group). All cases were recruited from the department of Pediatric Hepatology, Gastroenterology and Nutrition, National Liver Institute, Menofiya University. Those patients whose parents accepted to receive steroids were allocated in the steroids group; others were allocated in the control group. From each group a random sample was chosen using SPSS. An informed consent was signed by the parents of the steroid-treated patients before recruitment in the study which was approved by the Research Ethics Committee of National Liver Institute.

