### ***Statistical analysis plan (SAP)***

Quantitative data were presented as mean  $\pm$  standard deviation (SD) while qualitative data were presented as number and percentage. For both homogenously distributed and non homogenously distributed quantitative data, significance was tested by either independent samples *t*-test or by Mann-Whitney U test, respectively. Chi-square test or Fisher's exact test was used for the measurement of the qualitative data significance. Significance was set at *P* value  $< 0.05$ . A stepwise regression analysis was performed to examine independent factors associated with the outcome. Standardized regression coefficient ( $\beta$ ), 95% confidence interval (CI) and *P* values of each independent factor are presented. Statistical analysis was performed using SPSS, version 13 (SPSS Inc, Chicago, IL, USA).

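### Arm was set by parental acceptance over four years and no described analysis uses admission date, so the crude survival difference would absorb any joint drift in steroid uptake and prognosis

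*Combined protocol and SAP*

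**What the plan says.** Under Study population the document states "They were recruited over a period of 4 years duration and divided into two groups". The arm was not randomised: "Those patients whose parents accepted to receive steroids were allocated in the steroids group; others were allocated in the control group". A further step follows, with no reason or sampling fraction given: "From each group a random sample was chosen using SPSS". No calendar dates and no admissions per year are reported for either arm.

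The head count in the same section does not add up. It says "This study included 26 children with fulminant hepatitis A", then "Group one is comprised of 18 children with fulminant HAV infection" and "The second group is comprised of 15 children with fulminant HAV infection", which makes 18 + 15 = 33.

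The Statistical analysis plan offers unadjusted two-group tests and one multivariable step: "A stepwise regression analysis was performed to examine independent factors associated with the outcome". It names no covariates. Table 2 in the Results lists two candidates, steroid therapy and prothrombin time, and only steroid therapy was retained. The sentence below the table calls steroid therapy the sole independent factor for survival. Outcome assessment makes recovery or death the secondary response.

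**The concern.** When families choose the arm over several years, the share choosing steroids can change, and so can the background chance of survival. If both change, admission date is a confounder: one arm is weighted towards the period with better survival, and the pooled 2x2 table credits that to treatment. Adjusting for severity at presentation would not necessarily remove this, because a change in care acts after presentation.

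At stake is the reading of the main clinical result, a 57-point survival difference, and of Table 2, which a reader would take as evidence that the difference survives adjustment.

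**Working it through.** **1. Reproduce the reported figures.** Inputs from Table 1: survivors 15/18 (steroid) and 4/15 (non-steroid).

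- Pearson chi-square without continuity correction: 10.756, P = 0.00104, matching the printed 0.001. Fisher's exact two-sided P = 0.0016.
- Ordinary least squares of survival (0/1) on steroid alone: b = 15/18 − 4/15 = 0.567, 95% CI 0.268 to 0.865, P = 0.0005. The standardised coefficient is √(10.756/33) = 0.571.
- Table 2 prints 0.571, 0.268 to 0.865, P = 0.001. The coefficient is the standardised one, and the interval belongs to the crude risk difference. The estimate is therefore adjusted for nothing, admission date included.

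**2. What calendar time would have to do.** Split recruitment into an early and a late period and suppose steroids have no effect. The expected false difference in survival is

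(share of controls early − share of steroid children early) × (late survival − early survival).

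It is a product, so both factors must differ from zero. The documents give neither; the values below are assumptions.

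| Early controls v early steroid | Survival early → late | False difference |
|---|---|---|
| 14/15 v 2/18 | constant at 19/33 | 0.822 × 0 = 0.00 |
| 8/15 v 9/18 | 20% → 95% | 0.033 × 0.75 = 0.025 |
| 12/15 v 4/18 | 40% → 75% | 0.578 × 0.35 = 0.20 |
| 14/15 v 2/18 | 20% → 95% | 0.822 × 0.75 = 0.62 |

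In the third row the chance of Fisher P < 0.05 favouring steroids is 16%, and the chance of a difference of 0.567 or more is 1.3%. In the fourth row the chance of P < 0.05 is 98%. Moderate drift in both explains part of the observed gap; explaining all of it takes very steep drift in both.

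**3. Could a period-stratified analysis change the result?** Keep Table 1's margins (3 steroid and 11 control deaths), fix an assumed early/late split of each arm, and list every possible division of the deaths between periods. For each, compute the exact conditional stratified test (two-sided, summing outcomes no more probable than the one observed) and the Mantel-Haenszel risk difference.

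| Early controls v early steroid | Range of exact P | Range of risk difference |
|---|---|---|
| 9/15 v 7/18 | 0.0002 to 0.0052 | 64 to 45 points |
| 10/15 v 6/18 | 0.0004 to 0.013 | 67 to 35 points |
| 12/15 v 4/18 | 0.001 to 0.45 | 72 to 9 points |

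Doubling the one-sided P instead gives maxima of 0.0074 and 0.025 in the first two rows, so they stay below 0.05 either way.

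One case from the last row: deaths of 2/4 steroid v 10/12 control early and 1/14 v 1/3 late. The weights are 4×12/16 = 3.00 and 14×3/17 = 2.47. The risk difference is (3.00×0.333 + 2.47×0.262)/5.47 = 0.30, with P = 0.11. This needs overall mortality to fall from 12/16 = 75% to 2/17 = 12%. The extreme, P = 0.45, needs 14/16 = 87.5% to fall to zero.

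**The case against.** The strongest reply is that no drift is documented. Nothing says that care, survival or steroid uptake changed, and a reader might infer from the design that a time trend was in fact taken for a steroid effect. The documents do not support that; they leave the question open. This part of the objection stands, and the point is conditional for that reason.

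A reader might also think that drift in care or in uptake alone would be enough. It would not: the first two rows of the first table give false differences of 0.00 and 0.025.

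The Background offers a tempting size for the trend: "This 80% decreases to 30% when LT and artificial liver support system are available". That sentence compares settings without and with transplantation and artificial support, for non-acetaminophen failure in general. It is not a trend over time, not specific to hepatitis A and not about this centre, so it is not used here as evidence.

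Nor is this a historical-control design. One rule, accept or become a control, is described for one recruitment period, which is compatible with concurrent arms. It does not guarantee balance over time, and the random sample drawn from each group does not create it.

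Finally, with 14 deaths in 33 children a period-stratified test is a poor choice for the main analysis, and any cut point is somewhat arbitrary. That stands too. It argues for a sensitivity analysis, not for leaving time unexamined. The broader problem, that parents chose the arm, remains whatever the dates show.

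**Conclusion.** The point holds as a conditional one. Accrual took four years, the arm followed parental acceptance, and none of the analyses described in the SAP or shown in Tables 1 and 2 uses admission date. If both uptake and prognosis or care moved, the 57-point difference includes some of that movement, and Table 2 cannot separate it because it restates the crude difference. Whether this happened, and by how much, cannot be computed from the documents.

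The size depends on the overlap of the arms in time. Under the assumed two-period splits, imbalance up to 10/15 v 6/18 leaves the result significant for every division of deaths. At 12/15 v 4/18 significance can be lost, but only with a steep fall in overall mortality: P first passes 0.05, at 0.051, when mortality goes from 11/16 = 69% to 3/17 = 18%. The check could therefore either reassure or change the conclusion. All of this takes 18 and 15 as the analysed numbers, which the stated total of 26 contradicts.

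**What to change.** 1. Reconcile 26 with 18 + 15 = 33 and explain the random sample from each group. The date table depends on who was analysed.
2. Tabulate arm and deaths by year of admission. This assumes that admission dates are on record, which the documents do not say.
3. Beside the crude comparison, add a sensitivity analysis: a risk difference stratified by admission period with an exact stratified test. Fix the period boundaries before looking at outcomes by period.
4. Report how many children come from periods in which only one arm was recruited; they do not contribute to the stratified contrast.
5. Replace the sentence under Table 2 with one saying that the steroid estimate is unadjusted, and label the coefficient as standardised and the interval as that of the unstandardised coefficient.
6. State that good overlap in time would not remove confounding by parental choice.

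The cost is a change of SAP and results wording and a short re-analysis, if the dates exist. The downside is lower precision in the stratified estimate and the loss of children from one-arm periods.

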### ***Etiological diagnosis and group allocation***

Fulminant hepatitis A is defined by an acute onset of liver disease, due to HAV infection, with no known evidence of chronic liver disease, together with hepatic based coagulopathy (prothrombin time [PT]  $\geq 20$  seconds or international normalized ratio [INR]  $\geq 2.0$ ) that is not corrected by parenteral vitamin K and/or hepatic encephalopathy (must be present if the PT is 15–19.9 seconds or the INR is 1.5–1.9, but not if PT is  $\geq 20$  seconds or INR is  $\geq 2.0$ ) 5. After full investigations for possible etiologies, patients with proved etiology other than HAV or those with indeterminate FHF were not included.

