### ***Treatment regimen and modifications***

Patients were initially assigned to receive prednisolone at a dose of 1 mg/kg/d or its equivalent dose of methylprednisolone (0.8 mg/kg/d) for those who cannot take oral prednisolone (as patients with encephalopathy or vomiting). In those with improved PT (while on steroid therapy) below 20 seconds in conscious patients or below 15 seconds in encephalopathic patients, the steroid dose was maintained for further two weeks then withdrawal started. In those who had deterioration of liver functions upon withdrawal, treatment was continued for a longer duration till satisfactory biochemical improvement was achieved. The treatment was scheduled to be discontinued if uncontrollable hyperglycemia, gastrointestinal bleeding, or brain edema develops.

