### ***Outcome assessment***

The parameters of the primary response were improvement of PT followed by improvement of alanine transaminase and aspartate transaminase together with decreasing bilirubin during the period of observation. The overall clinical outcome (recovery or death) was

considered secondary response parameter. Treatment tolerability and side effects were also monitored.

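### Groups are defined both by steroid receipt and by parental acceptance, with no common time zero, so deaths before a first dose or before a decision can fall to the control group

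*Combined protocol and SAP*

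**What the plan says.** The Study population section gives two rules for group membership.

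- **By treatment received.** The first sentence on the treated group reads "Group one is comprised of 18 children with fulminant HAV infection who received steroid therapy beside standard supportive measures (steroid group". The comparison group is "15 children with fulminant HAV infection who did not receive steroid therapy, but only standard supportive measures (non steroid group".
- **By parental decision.** "Those patients whose parents accepted to receive steroids were allocated in the steroids group; others were allocated in the control group".

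The section does not say which rule governs when they differ.

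On timing, the text gives only fragments. For treated children, "An informed consent was signed by the parents of the steroid-treated patients before recruitment in the study"; no entry point is given for controls. Etiological diagnosis and group allocation makes inclusion depend on a work-up of unstated length: "After full investigations for possible etiologies, patients with proved etiology other than HAV or those with indeterminate FHF were not included". Outcome assessment follows children "during the period of observation", with neither start nor length stated. It treats survival as a yes/no secondary response: "The overall clinical outcome (recovery or death) was" secondary to the laboratory measures.

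The SAP section compares groups by chi-square or Fisher's exact test and by stepwise regression. Results, Table 1, reports 15 of 18 steroid children and 4 of 15 controls living (P = 0.001). It gives a steroid duration of 5 to 50 days, median 22.

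**The concern.** If a child can die between becoming eligible and being classified, the way that child is counted matters. Under the receipt rule, a steroid child must have lived to a first dose, while a control need not have lived to any particular point. Deaths in that interval then fall on the control side whatever steroids do. This is the usual mechanism of immortal-time bias, and here it would favour steroids.

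At stake is the survival difference and the statement under Table 2 that steroid therapy was the only independent parameter associated with survival. Adding baseline covariates to a regression does not repair time that has been assigned to the wrong group.

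**Working it through.** **1. Where the two rules agree and differ**

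| Child | Receipt rule | Acceptance rule |
|---|---|---|
| Parents accepted, dosed | Steroid | Steroid |
| Parents declined | Control | Control |
| Parents accepted, died before a first dose | Control | Steroid |
| Died before parents were asked | Control | Control |

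The rules conflict only in the third row. The fourth row is a separate problem: both rules make that child a control, although no decision was ever made.

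**2. Reproducing the reported figures**

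Table 1 gives living/dead as 15/3 (steroid) and 4/11 (control), N = 33. The Pearson statistic without continuity correction is

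N(ad − bc)² / (product of the four margins) = 33 × (15×11 − 3×4)² / (18×15×19×14) = 33 × 153² / 71,820 = 10.76, so P = 0.00104.

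This matches the printed 0.001. Fisher's exact test (two-sided) gives P = 0.0016. The difference in the proportion living is 83.3% − 26.7% = 56.7 points before rounding.

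A plain linear regression of living (1/0) on steroid (1/0) gives a standardised coefficient of 153/√71,820 = 0.571 and an unstandardised 95% CI of 0.268 to 0.865, as printed in Table 2. So Table 2 uses the same two fixed groups with no time element.

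**3. Sensitivity range**

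The number of affected deaths, k, is not in the documents; it is an assumption varied here. Two-sided tests are also assumed. Accepted-but-undosed deaths would *move* to the steroid group, giving 15/(18+k) v 4/(15−k) living. Deaths before a decision would be *excluded* from the controls, giving 15/18 v 4/(15−k).

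| Scenario | Living, steroid v control | Difference (points) | Fisher P | Chi-square P |
|---|---|---|---|---|
| As reported | 15/18 v 4/15 | 56.7 | 0.0016 | 0.0010 |
| Move 1 | 15/19 v 4/14 | 50.4 | 0.006 | 0.004 |
| Move 2 | 15/20 v 4/13 | 44.2 | 0.029 | 0.012 |
| Move 3 | 15/21 v 4/12 | 38.1 | 0.066 | 0.033 |
| Move 4 | 15/22 v 4/11 | 31.8 | 0.136 | 0.081 |
| Move 8 | 15/26 v 4/7 | 0.5 | 1.000 | 0.979 |
| Exclude 5 | 15/18 v 4/10 | 43.3 | 0.035 | 0.019 |
| Exclude 6 | 15/18 v 4/9 | 38.9 | 0.072 | 0.037 |
| Exclude 7 | 15/18 v 4/8 | 33.3 | 0.149 | 0.077 |

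Check of one row (move 3): 33 × (15×8 − 6×4)² / (21×12×19×14) = 33 × 96² / 67,032 = 4.54, P = 0.033.

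The SAP permits either test and gives no rule for choosing between them, so both are shown. The 0.05 line is crossed at 3 moved deaths by Fisher and 4 by chi-square, or at 6 excluded by Fisher and 7 by chi-square.

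**The case against.** The strongest reply is that the text permits this bias but does not show it. No date of death, no interval from eligibility to first dose and no count of undosed children is given, so the number of affected deaths may be zero. The sentence that speaks of allocation uses the parents' decision; on that reading the receipt wording merely describes the groups, and accepted-but-undosed children stay in the steroid group. Survival is also a secondary response. And 6 of 11 control deaths (55%) would have to be removed before Fisher's test passes 0.05. All of this stands as a limit on size. It does not close the gap, because the text never says which rule was applied, and the never-asked child is a control on either reading.

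Three stronger readings are tempting and are not supported.

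- *The 5-day minimum steroid duration proves immortal time.* It is an observed duration after the first dose, when children were already at risk. No section makes it an entry condition. With only three steroid deaths it could be chance, and an early benefit would look the same. It is compatible with the bias but is not evidence of it.
- *The two definitions conflict for every early death.* They conflict only for the accepted-but-undosed child.
- *Three misplaced deaths remove significance.* That holds for Fisher's test only; the chi-square test, which reproduces the printed P, still gives 0.033.

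**Conclusion.** The point holds as a defect of definition: two classification rules, no common time zero, and an analysis that treats steroid use as a fixed label from the start. Together they allow deaths before a dose or before a decision to be counted against the control group, and the planned tests and regression cannot correct that. The direction, if it operates, favours steroids.

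The size is unknown. The range in the table rests on an assumed number of affected deaths. One or two moved deaths would reduce the 56.7-point difference to 50.4 or 44.2 points and leave P below 0.05; 3 to 4 moved, or 6 to 7 excluded, would take it past 0.05 depending on the test. A reader might infer that the survival difference is an artefact of timing. The documents do not support that; they support only that it cannot be ruled out from what is written.

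Confounding by parental choice is a separate problem and is not addressed by this point. Nor is the mismatch between the 26 children stated in Study population and the 18 + 15 = 33 analysed.

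**What to change.** **Study population.** Set time zero, in both groups, at the date the criteria in Etiological diagnosis and group allocation were first met. Classify every eligible child by the parents' decision and keep accepted-but-undosed children in the steroid group. Report separately the number and outcome of children who died before a decision was sought, and do not count them as control deaths. Both groups are then conditioned alike on having reached a decision.

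**SAP section.** Add one sensitivity analysis, kept distinct from the decision-based comparison: either a survival model from time zero with steroid start as a time-dependent covariate, or a landmark analysis. A landmark should be chosen from the usual interval between eligibility and decision. It should not be taken from the shortest observed steroid duration: that choice comes from the treated group's own data, and it would also drop valid control deaths among children whose parents had already declined.

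**Results.** If the dates cannot be retrieved, state that the survival comparison is open to this bias and soften the conclusion under Table 2.

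**Cost.** A few sentences of text, chart retrieval of the eligibility, decision, first-dose and death dates, and a somewhat wider interval. If no such deaths exist, reporting that fact removes the doubt.

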## Results

**Table 1:** Outcome of steroid therapy

Characteristics	Steroid (n = 18)	Non-Steroid (n = 15)	P-value
Type of steroids			
Methylprednisolone	10 (55.6)	--	
Prednisolone	8 (44.4)	--	
Duration of steroids (days)			
Minimum-Maximum (median)	5 – 50 (22)	--	
Outcome			
Living	15 (83.3)	4 (26.7)	0.001
Dead	3 (16.7)	11 (73.3)	

[figure not shown]
Number of living patients were significantly higher in the steroid group compared to non-steroid group

**Table 2:** Stepwise regression analysis for parameters with significance between living and dead patients

Characteristics	$\beta$	P-value	95% CI	
			Lower	Upper
Steroid therapy	0.571	0.001	0.268	0.865
Prothrombin time (seconds)	NI	--	--	--

$\beta$ : regression coefficient; CI: confidence interval; NI: not included

Steroid therapy was the only independent parameter associated with survival of patients

**Figure 1.** Serial changes of prothrombin time (A) and total bilirubin (B) in the steroid group.

PT: prothrombin time

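### Parental choice fixed the arm, the random draw was made within arms, and the steroid effect that Table 2 calls independent is the unadjusted comparison

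*Combined protocol and SAP*

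**What the plan says.** The Study population section is open about how the groups arose: "Those patients whose parents accepted to receive steroids were allocated in the steroids group; others were allocated in the control group". It then adds "From each group a random sample was chosen using SPSS". It gives neither the number of children each group was sampled from nor whether the draw came before or after outcomes were known.

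On numbers, the section opens with "This study included 26 children with fulminant hepatitis A", continues "Group one is comprised of 18 children with fulminant HAV infection who received steroid therapy", and gives 15 children for the second group. Consent is described for one arm: "An informed consent was signed by the parents of the steroid-treated patients".

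The SAP section plans the multivariable step as follows: "A stepwise regression analysis was performed to examine independent factors associated with the outcome". It says that standardised coefficients with 95% CIs will be shown. It names no covariate to be kept in the model whatever the selection result.

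In Results, Table 1 gives 15 of 18 alive with steroids and 4 of 15 without. Table 2, titled "Stepwise regression analysis for parameters with significance between living and dead patients", lists steroid therapy (coefficient 0.571, P 0.001, 95% CI 0.268 to 0.865) and marks PT as not included. The text below it concludes: "Steroid therapy was the only independent parameter associated with survival of patients".

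**The concern.** When families choose the arm, children in the two arms may differ in ways that also affect survival. Random sampling within each arm decides only which children are analysed, not which treatment they receive. In expectation it leaves any difference between accepting and declining families unchanged.

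Protection then has to come from the analysis. A reader who sees that steroid therapy was the only independent parameter will take the estimate to be adjusted for PT, because PT is the other row of the table. If the final model has steroid therapy as its only term, the estimate is adjusted for nothing, and the 57-point survival difference carries whatever imbalance parental choice produced. Failure of PT to enter a stepwise model with 33 children and 14 deaths does not show that severity was balanced or controlled.

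**Working it through.** **Inputs.** Table 1: steroid arm 15 alive, 3 dead (18); non-steroid arm 4 alive, 11 dead (15); in total 19 alive, 14 dead, n = 33. Table 2: 0.571, P 0.001, 95% CI 0.268 to 0.865.

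**Step 1: reproduce Table 2 with no covariate.** Ordinary least squares of survival (1/0) on arm (1/0):

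- Difference = 15/18 − 4/15 = 0.8333 − 0.2667 = 0.5667.
- Residual sum of squares = 15×3/18 + 4×11/15 = 2.500 + 2.933 = 5.433. Residual variance = 5.433/31 = 0.1753.
- SE = √[0.1753 × (1/18 + 1/15)] = 0.1464.
- 95% CI = 0.5667 ± 2.0395 × 0.1464 = 0.268 to 0.865; P = 0.0005, which is 0.001 to three decimals.
- Standardised coefficient (phi) = (15×11 − 3×4)/√(18×15×19×14) = 0.571.

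Every figure in the steroid row of Table 2 follows from the four counts in Table 1. The final model therefore contains arm and nothing else.

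**Step 2: scale.** The printed interval has midpoint (0.268 + 0.865)/2 = 0.5665, which is the unstandardised difference and not 0.571. The standardising factor is √(18×15)/√(19×14) = √(270/266) = 1.0075. On the standardised scale the interval would be about 0.270 to 0.872. The mismatch is numerically small, but it confirms which model was fitted, and the estimate and the interval answer different questions.

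**Step 3: how strong would confounding have to be?** The documents give no patient-level covariates, so an adjusted estimate cannot be computed. What can be computed is the strength of unmeasured confounding needed:

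- Death risk ratio = (3/18)/(11/15) = 0.227.
- SE of the log = √(1/3 − 1/18 + 1/11 − 1/15) = 0.550; 95% CI 0.077 to 0.667.
- E-value for the estimate: 1/0.227 = 4.40; 4.40 + √(4.40 × 3.40) = 8.3.
- E-value for the limit: 1/0.667 = 1.50; 1.50 + √(1.50 × 0.50) = 2.4.

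A factor associated with both arm and death by risk ratios of about 2.4 each could bring the interval to no effect. About 8.3 each would be needed to explain the whole estimate.

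**Step 4: counts.** 18 + 15 = 33, not 26. Table 1 uses 18 and 15 as denominators, and Table 2 reproduces at n = 33, so 26 is not the number analysed. Being smaller than 33, it cannot be the pool from which 33 were drawn.

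**The case against.** The best defence is that nothing is concealed. The document says plainly that parents chose, and nowhere calls the SPSS draw allocation or randomisation. A reader might infer that a randomised comparison is being claimed; the text does not support that. Survival is also only the secondary response parameter, and the data are already collected, so the design cannot be changed. All of this stands. What it leaves untouched is the wording of the conclusion under Table 2.

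Three stronger readings are tempting and should be resisted.

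- **PT must have been imbalanced between arms**, because it separated living from dead yet did not enter after steroid therapy. This does not follow. The SAP allows either a t-test or a Mann-Whitney test for single-factor comparisons. Skewed PT values can be placed on the Table 1 records so that PT passes the Mann-Whitney screen, does not enter after steroid therapy, and shows no adverse imbalance; adjusted differences were then 0.565 to 0.585, against 0.567 crude. Table 2 also does not say whether its PT is an entry value. PT improvement is part of the primary response, so an on-treatment PT could differ by arm because of treatment.
- **The steroid difference is overstated.** It may be, but neither the direction nor the size of confounding can be recovered from the documents.
- **Sampling threw away precision.** The fraction kept is not given and may be 100%. Another possible reading is that 33 was the pool and 26 the draw, in which case Table 1 covers everyone.

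Parts of the document were not available for this review, so baseline data may exist there. That would not alter Table 2, whose figures are those of the crude comparison.

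**Conclusion.** The point holds in this form. Arm was set by parental choice, the only random step described operates within arms, and the estimate offered as independent is the unadjusted difference of 57 percentage points (95% CI 27 to 87) at n = 33, with its coefficient and interval on different scales. The phrase about the only independent parameter is therefore not an adjusted conclusion. The E-values (8.3 and 2.4) say how strong confounding would have to be; they do not show that it is present. The stated total of 26 is inconsistent with the two group sizes and with the tables.

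The identification of the model rests on agreement to three decimals between Table 2 and a one-predictor linear fit to Table 1. It needs no assumption about PT. The change is worth making because it alters how the survival result may be described, though it does not show that result to be wrong.

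**What to change.** 1. Refit survival on steroid therapy with entry PT kept in the model regardless of stepwise selection. Report the estimate and its CI on the same scale, and show entry severity by arm. This assumes that entry PT is held for all 33 children.
2. Replace the statement that steroid therapy was the only independent parameter with a description of a non-randomised association in groups formed by parental choice.
3. Reconcile the stated 26 children with 18 + 15 = 33. State how many eligible children each group was sampled from and whether the draw preceded knowledge of outcome. If any were sampled out and their records may be used, analyse all of them.

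**Cost.** Items 1 and 2 need one refit, one table and a change of wording. Item 3 is a correction and a short statement, unless children were sampled out. In that case it needs record retrieval and an ethics step, since the section describes consent only from parents of steroid-treated children. The interval may widen, 14 deaths support about one covariate, and self-selection on unmeasured factors remains after adjustment for PT.
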